In IVF cycles, basal serum AMH level was significantly correlated with AFC, the number of follicles obtained after stimulation and the number of retrieved oocytes, and has been found useful in prediction of suboptimal and excessive ovarian responses upon ovarian stimulation (Ficicioglu et al, 2006; Lekamge et al, 2007; Kwee et al, 2008; Broer et al, 2009; Ledger, 2010; Broer et al, 2011). It has been suggested that measurement of serum AMH can be used for patient-tailored individualization of the dosage of gonadotrophin used in ovarian stimulation during IVF treatment (Olivennes et al, 2009; Nelson et al, 2009; Yates et al, 2011). Compared to AFC, AMH has the advantage of having less intra- and inter-cycle variation (van Disseldorp et al, 2010) and is not operator-dependent, despite its additional cost. However, there is yet no prospective randomized trial to compare the performance of AFC and AMH in this regard.

Therefore, we propose this randomized trial to evaluate the role of baseline serum AMH and AFC for determination of gonadotrophin dosing in in-vitro fertilization treatment.

3. Objectives:

This is a prospective randomized trial to compare the use of AFC and serum AMH as the basis for gonadotrophin dosing in in-vitro fertilization treatment.

The hypothesis is that the use of serum AMH as the criterion for determination of gonadotrophin dosing in IVF treatment results in more optimal ovarian response than AFC.

4. Study design:

Patients undergoing the first-time IVF treatment cycle using either conventional insemination technique or intracytoplasmic sperm injection at Queen Mary Hospital will be invited to participate in this study. Participating subjects will be randomized into either (i) AFC or (ii) AMH group, where the gonadotrophin dosing will be determined based on the baseline AFC and serum AMH respectively as assessed one month before the IVF treatment.

Randomisation will be performed according to a computer-generated list which will be read by an independent research nurse. That research nurse will assign the initial gonadotrophin dose according to the study protocol. The clinician and patient will both be blinded to the randomization throughout the course of treatment. The proportion of subjects having appropriate ovarian response, defined as the number of oocytes retrieved being 6 to 14 inclusive (Broer et al, 2010), will be compared between the two arms.

5. Subject selection and exclusion

5.1 Inclusion criteria:

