- Subjects undergoing the first IVF cycle during the study period.

5.2 Exclusion criteria:

- Body mass index ≥ 30 kg/m²
- Subjects in repeated IVF cycles
- Subjects undergoing IVF treatment using donor oocytes
- Subjects undergoing pre-implantation genetic diagnosis

6. Treatment of subjects

Subjects will attend the Assisted Reproduction Clinic on day 2-5 of the menstrual cycle preceding their scheduled IVF treatment. They will undergo transvaginal ultrasound examination to determine the AFC and assess for other pelvic abnormalities as what would be routinely done before IVF according to our usual protocol. **Blood (10 c.c.)** will also be taken for measurement of reproductive hormones including FSH, LH, E2 and AMH. The subjects will be asked for separate consent to archive the residual serum samples for future studies on reproductive endocrinology as appropriate (such future studies will be subject to approval by the HKU/HA HKWC IRB).

Subjects will be interviewed by a dedicated research nurse to explain on this study. Those who give written informed consent will be randomized into either the AMH or AFC groups according to a computer-generated randomization list.

(All participants will be blinded to AFC during ultrasound examination. A research nurse will keep the ultrasound sheets of all patients separately, which will be filed back to the patients' medical record upon completion of the ovarian stimulation.)

In their IVF treatment cycle, the ovarian stimulation regimen will be determined according to the randomization result as per the following table:

Gonadotrophin (FSH or HMG) regimen	AMH Group	AFC Group
300 IU daily	AMH ≤ 1.0 ng/ml	AFC ≤ 5
225 IU daily	AMH >1.0 and ≤ 3.3 ng/ml	AFC >5 and ≤ 15
150 IU daily	AMH >3.3 ng/ml	AFC >15

The AMH cut-off values are based on review of 214 patients previously treated in our centre who had AMH and AFC determined before ovarian stimulation. By regression

analysis, an AMH value of 1.0 ng/ml and 3.3 ng/ml corresponded to AFC of 5 and 15 respectively. Both linear and quadratic regression models gave roughly the same results.

The dose will be charted by the research nurse, and both the clinician and the patient will be blinded to the assigned group.

All subjects will be assessed by transvaginal ultrasound scan on the 7th day of ovarian stimulation, with the dose of gonadotrophin adjusted according to the ovarian response as detailed in the following table:

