Response category	Criteria based on the number of follicles >10 mm (F10)	Action on gonadotrophin dose
Under-response	F10 ≤5	Step-up the dose: 150 → 225 IU daily, or 225 → 300 IU daily
Normal response	F10 >5 and ≤15	Keep at same dose
Excessive response	F10 >15	Step-down the dose: 225 → 150 IU daily 150 → 112.5 IU daily

The dose adjustment will be made for **once only** throughout the treatment cycle.

All subjects will be treated on a GnRH antagonist protocol for pituitary down-regulation. They will receive **cetorelix or ganirelix** 250 microgram subcutaneous injection starting from the 6th day of ovarian stimulation until the day of hCG trigger, according to our current clinic protocol.

Human chorionic gonadotrophin (hCG) will be administered for ovulatory trigger when the leading follicle reaches 18 mm, with preferably two or more other follicles reaching 16 mm in mean diameter. Oocyte retrieval will be carried out 34-36 hours post-hCG, where all follicles >10 mm will be aspirated.

All subjects will proceed to hCG trigger and oocyte retrieval except for those with zero follicle developing to beyond 10 mm after 12 days of stimulation, or when these are contraindicated for other medical reasons. Any events of ovarian hyperstimulation syndrome (OHSS) or anticipated risk of OHSS will be managed according to current practice.

7. Study outcomes

Primary outcome:

- Percentage of subjects having appropriate ovarian response (defined as number of oocytes retrieved being between 6 and 14).

Secondary outcome:

- Percentage of subjects requiring step-up or step-down of gonadotrophin dose upon first ultrasound tracking.

Hormone assay:

AMH concentration will be determined with ELISA using a commercial automated method (Access AMH Assay, Beckman-Coulter, Texas, USA), which has a limit of detection of 0.02 ng/ml.

8. Statistics

8.1 Statistical tests:

The percentage of subjects having appropriate ovarian response, defined as number of oocytes retrieved between 6 and 14 (Broer et al, 2010), as well as the percentage requiring step-up and step-down of gonadotrophin dose, will be compared between the AMH and AFC groups using χ^2 test or Fisher's Exact test as appropriate. Statistical analyses will be performed using the SPSS software.

8.2 Sample size estimation:

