According to review of our Centre's data (unpublished), 50% of our patients have appropriate ovarian response when using AFC to determine gonadotrophin dosing as in current practice. Assuming that an increase to 70% of appropriate response in the AMH group will be clinically significant, we require a minimum of 93 subjects to demonstrate a significant difference between the AMH and AFC groups with 80% power and type I error of 0.05. To allow for drop-outs, a total of 200 subjects (i.e. 100 per group) will be recruited.

9. Assessment of safety

There is no safety concern as the study does not involve any extra medical intervention to the patients concerned. It only involves the comparison of two assessment tools for determination of gonadotrophin dosing. The use of AFC for this purpose is the current practice in our Centre, whereas the use of AMH for this purpose is well supported in recent literature.

10. Direct access to source data / documents:

Trial-related monitoring, audits and regulatory inspections are allowed.

11. Quality control and quality assurance

This shall follow the general quality control policy established for our clinic as well as for our hormone assay laboratory.

12. Ethics:

Ethics approval will be applied for before commencement of study.

13. Data Handling and record keeping

All data will be stored and analysed using SPSS. All the investigators will be responsible for data management including data coding, monitoring and verification.

14. Financing and insurance

The study will be funded by the Department of Obstetrics and Gynaecology, University of Hong Kong.

15. Publication policy

The findings of this study will be submitted for consideration for publication in peer-reviewed scientific journal.

16. Supplements

Nil

References:

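### Allocation can change the starting gonadotrophin dose, yet section 9 sees no safety concern and the plan reports neither more than 14 oocytes nor OHSS by arm

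*Combined protocol and SAP*

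**What the plan says.** Section 9 (Assessment of safety) gives its reason in two sentences: "There is no safety concern as the study does not involve any extra medical intervention to the patients concerned", and "It only involves the comparison of two assessment tools for determination of gonadotrophin dosing". It adds that dosing by AFC is the centre's current practice and that the literature supports dosing by AMH.

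Section 6 (Treatment of subjects) says that "the ovarian stimulation regimen will be determined according to the randomization result as per the following table". The table gives 300, 225 or 150 IU daily, by AMH band in one arm (cut-offs 1.0 and 3.3 ng/ml) and by AFC band in the other (cut-offs 5 and 15). The cut-offs were matched by regression in 214 earlier patients, where "an AMH value of 1.0 ng/ml and 3.3 ng/ml corresponded to AFC of 5 and 15 respectively". Both arms follow the same day-7 rule for a single dose adjustment. On OHSS, section 6 says only: "Any events of ovarian hyperstimulation syndrome (OHSS) or anticipated risk of OHSS will be managed according to current practice".

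The primary outcome in section 7 is "Percentage of subjects having appropriate ovarian response (defined as number of oocytes retrieved being between 6 and 14"). The one secondary outcome is the percentage needing step-up or step-down at the first scan. Section 8.1 plans between-arm tests of these and nothing else.

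**The concern.** The trial's hypothesis can only work through dose. If AMH gives a better response than AFC, it does so because some women start on a different dose than they would have had in the other arm. A safety section that rests on the absence of an extra intervention leaves this out.

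The gap carries into the reporting. The background, before section 3, says that AMH "has been found useful in prediction of suboptimal and excessive ovarian responses upon ovarian stimulation", so it names two kinds of poor result. They have different consequences: a low response yields few oocytes, while an excessive one carries the OHSS risk that section 6 anticipates. The primary outcome merges them. If the plan is followed exactly, the report could conclude that ovarian response was more optimal under AMH with no by-arm view of final excessive response or of its main harm.

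**Working it through.** **1. Dose differences that allocation can cause (section 6 table).** Adjacent bands: 300 − 225 = 75 IU and 225 − 150 = 75 IU daily. Opposite bands: 300 − 150 = 150 IU daily. Same band: 0.

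**2. The plan's own figure (section 8.2).** Inputs: 50% against 70%, 80% power, type I error 0.05 (taken as two-sided). Pooled formula without continuity correction:

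n = [1.96·√(2·0.6·0.4) + 0.8416·√(0.5·0.5 + 0.7·0.3)]² / 0.20² = (1.358 + 0.571)² / 0.04 = 93 per group.

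This reproduces the stated 93, and nothing below changes it.

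**3. What the target implies about dose changes.** Section 8.2 reads: "Assuming that an increase to 70% of appropriate response in the AMH group will be clinically significant". Women in the same band under both markers get the same starting dose and the same day-7 rule in either arm, so they contribute no difference. Let s be the share in different bands and g the net gain among them:

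0.70 − 0.50 = s·g, with g ≤ 1, so s ≥ 0.20.

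That is at least 0.20 × 200 = 40 women if the target is met. With g = 0.5 (an assumption), s = 0.40, or 80 women. This shows that the plan's target requires allocation to determine dose for a sizeable group. It says nothing about the direction or amount of harm.

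**4. What the primary outcome can hide.** In each arm the shares with 6-14 oocytes, more than 14, and all other results (fewer than 6 or no retrieval) sum to 100%.

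- AFC arm at 50%: more than 14 can be anything from 0% to 50%.
- AMH arm at 70%: more than 14 can be anything from 0% to 30%.

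The change in more than 14 is −20 points minus the change in all other results. Excess can therefore rise only if the other non-appropriate results fall by more than 20 points. An illustration with assumed counts per 100 (low / 6-14 / high):

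| Arm | <6 | 6-14 | >14 |
|---|---|---|---|
| AFC | 25 | 50 | 25 |
| AMH, case A | 20 | 70 | 10 |
| AMH, case B | 0 | 70 | 30 |

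Cases A and B give the same primary test: χ² = 200·(70·50 − 30·50)² / (100·100·120·80) = 8.33. Excess falls by 15 points in A and rises by 5 in B. Case B is extreme, but the primary table could not tell it from A.

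**5. What the secondary outcome adds.** Step-down is triggered by more than 15 follicles above 10 mm on day 7. That gives some direction by arm, but it is a count before trigger, not oocytes retrieved or OHSS. The table lists 225 to 150 and 150 to 112.5 IU; it lists no step-down from 300 IU.

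**6. Precision of by-arm safety tables at 100 per arm.** The documents give no OHSS or >14 rate, so the counts are assumed.

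- 0/100, exact upper limit: 1 − 0.025^(1/100) = 3.6%, so the 95% CI is 0 to 3.6%. For 2/100 it is 0.2% to 7.0%.
- 2 against 4 events (Newcombe; Wilson limits 0.55 to 7.00 and 1.57 to 9.84): lower 2 − √(2.43² + 5.00²) = −3.6; upper 2 + √(5.84² + 1.45²) = 8.0. Difference +2 points (−3.6 to 8.0).
- More than 14 oocytes, 25 against 15 per 100, same method: −10 points (−20.9 to 1.1).

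These support description, not testing.

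**The case against.** The strongest reply is that section 9 is accurate as worded. No drug, visit or procedure is added, and the section itself says that the tools determine gonadotrophin dosing. A reader might infer that sections 6 and 9 contradict each other; on the ordinary sense of extra, they do not. What stands against section 9 is narrower: it never says that the dose a given woman receives can depend on her arm.

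Care is also protected. Both arms use the same three doses, an antagonist protocol, a day-7 scan with a step-down rule, and routine OHSS management. Step-down is compared by arm. All of this stands, and it makes the point one of rationale and reporting, not of patient care.

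A reader might go further and infer that AMH dosing is likely to cause more OHSS. Nothing in the documents shows this. A 20-point rise in 6-14 is a 20-point net fall in everything else, and excess may well fall too.

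The opposite inference is equally unsupported: that regression-matched cut-offs mean no shift in average dose. Section 6 does not say which marker was regressed on which, and matched cut-offs do not guarantee equal band shares. Nor can the actual share of women in different bands be estimated, because neither the correlation between the markers nor the band shares are given.

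Finally, OHSS tables at this size will be imprecise. That is true, and it is why no formal test is proposed.

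**Conclusion.** The point holds as a cheap improvement to safety reporting and to what the trial can conclude. It is not a flaw in the primary test or the sample size, and it does not show excess harm in either arm.

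Allocation changes the starting dose by 75 or 150 IU daily for women whose bands differ. The number of such women is not given; the bound of at least 40 of 200 applies only if the 50% to 70% target is met and same-band women respond alike in both arms. Under the plan as written, a result at the target is compatible with anything from 0% to 30% of the AMH arm having more than 14 oocytes. OHSS would not appear by arm at all. Day-7 step-down fills part of this gap, not all of it.

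**What to change.** 1. **Section 9:** state that allocation adds no new drug or procedure but can change the starting gonadotrophin dose for women whose AMH and AFC bands differ.
2. **Beside the primary result:** report fewer than 6, 6-14 and more than 14 oocytes by arm. Give women without retrieval their own row with the reason, so that a cycle stopped for OHSS risk is not read as a low response.
3. **Section 7:** add descriptive safety outcomes by arm over all randomised women, as counts with 95% CIs and no formal test. These are OHSS by severity, using one classification named in the protocol over the clinic's routine follow-up and ascertained alike in both arms, and cycles cancelled or modified for OHSS risk.

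The oocyte split uses counts that the primary outcome already needs. OHSS needs a named classification and a little extra recording, which the protocol does not now describe. The downside is a few low-precision tables that could be over-read, which giving intervals instead of p-values limits. Treatment, sample size and the primary test stay as they are.
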